Falls in community-dwelling older adults are a major public health issue with an annual incidence of approximately 30% among adults aged \geq 65 years increasing to 32-42% among those aged \geq 75 years (1). In addition, the number of fallers is expected to increase in the future since the proportion of older people over 60 years is increasing worldwide (2). In Europe, the most frequent reason for older adults to contact an emergency department is due to falls - accounting for 50% of the total contacts (3). Even though most of the falls result in minor injuries, an increasing proportion leads to fractures or hospitalization. Furthermore, consequences of falls include increased morbidity and mortality along with loss of independence, which may lead to early institutionalization (1,4,5). Finally, the increasing number of fallers also leads to increased financial burden on the health care system (6).

Although some falls have a single obvious reason, most falls have a multifactorial aetiology such as previous falls, advanced age, cognitive impairment, environmental risks, hazardous activities, along with presence of chronic disease, muscle weakness, gait and balance disorders, and medication use (1,4,7–13). Recently, The European Geriatric Medicine Society (EuGMS) Task and Finish Group published a consensus paper classifying 14 medication classes as fall-risk-increasing drug (FRID) (14). Most of them were psychotropics, but several new possible FRIDs were identified. However, the group did not reach consensus on 17 medication classes as potential FRIDs (antihypertensives, cardiac glycosides, antiarrhythmics, gastrointestinal agents, central nervous system agents, chemotherapeutics, hypoglycaemics, fluoroquinolones, corticosteroids, and nonsteroidal anti-inflammatory drugs). This was substantiated by the studies presented for the panellists being heterogenous due to various settings, different cohorts of older adults as well as unclear descriptions of the medication and falls ascertainment methods. Hence, the evidence was insufficient to attain consensus.

This is consistent with the current gap in the literature with only a few studies investigating fall risk related to these types of drugs (15–17). Moreover, the group advocated for a higher research quality in primary studies due to issues with precise definitions of target medications and falls as well as lack of controlling for confounders (14,18). Therefore, to achieve a better understanding of these 17 medication classes as potential FRIDs, more studies taking these issues into account are warranted.

Primary objective:

To examine the association between use of the potential FRIDs and falls rate with a 1-year followup in a cohort of community-dwelling older adults, aged 75 years or more.

Study methods

Study design and sample size:

This prospective cohort study builds on previous data from the PREFALL study conducted in cooperation with Hjørring Municipality, Denmark (19). A pre-registered protocol on the PREFALL study was accepted at Clinicaltrials.gov (NCT03608709) on 01/08/2018 (20). The study recruited participants from 14/06/2018 to 18/07/2019 and had a 1-year follow-up period. The sample size was derived without a recommended power calculation; hence, the sample size builds on feasible recruitment within the 13 months inclusion period granted by the municipality due to economical and administrative reasons.

Timing of final analysis:

All study data were accessible from the PREFALL study before the completion of this protocol. Therefore, a detailed statistical analysis plan for this study was prepared before any outcome analysis was conducted to provide transparency on the intended and pre-planned analysis. This is prespecified later in the protocol.

Study population and setting

The participants were community-dwelling aged 75 or more. Participants were excluded if they had 1) a dementia diagnosis; 2) acute illness defined by the presence of a participant-reported experience of illness within 7 days before inclusion affecting their ability to participate in social activities outside their homes; 3) inability to understand Danish; 4) Unable to stand unassisted for one minute. Support was defined by any assistive devices or help from another person. In Denmark, municipalities develop and initiate prophylactic and health-promoting initiatives for senior citizens (22). Thus, the participants were recruited through preventive home visits (PHV), senior activity centres (SAC), along with senior clubs and associations in Hjørring Municipality, Northern Jutland, Denmark. For PHVs, all the community-dwellers aged 75+ years who accepted the invitation to PHV were assessed for eligibility and included consecutively. For SACs, senior clubs, and senior associations, participants were conveniently recruited by oral study presentations since a

consecutive sampling method was not possible due to varying attendees each day. Lastly, recruitment videos were transmitted by the local televisions channel along with ads in newspapers and social media. For a more detailed description of the study setting and recruitment, the investigators refer to the PREFALL study (19).

Follow-up:

Follow-up time will be defined as the time from inclusion until death, withdrawal, or end of the study at the 18/07/2020. A summary of the participants' loss to follow-up will be presented with reasons and baseline characteristics to describe the adequacy of follow-up.

Baseline characteristics:

Data collection was performed at baseline and based on a multifactorial falls risk test battery including various physical tests (static balance under dual-task conditions, grip- and lower limb strength, reaction time of lower limbs and gait speed); self-report questionnaire on sociodemographic characteristics, frailty, nutrition, disability, fear of falling, health-related quality of life, depressive symptoms, several physical symptoms, cognitive tests; and reporting of comorbidities (23). The participants' comorbidities were obtained from the participants' hospital records and the diagnoses were indexed according to the International Classification of Diseases 10th revision (ICD-10). For a more detailed description of physical test and self-report questionnaire and their rationale, the investigators refer to the PREFALL study (19).

Baseline medication:

To determine the participants' medications at inclusion, the investigators consulted the national Shared Medication Record (SMR). The SMR is a national registry of current medication use and pharmacy records of prescriptions to each citizen in Denmark. Any physician involved in the patients' clinical course has access to the SMR data and all details of each prescription and the date of the latest medication reconciliation are provided (24). For each participant all medication registered in SMR at baseline was documented and indexed according to the WHO-recommended anatomical therapeutic chemical (ATC) medication classification system. The potential FRIDs which will be investigated in this study are: Beta-blockers (C07A); angiotensin-converting enzyme (ACE) inhibitors (C09A); calcium channel blockers (C08); cardiac glycosides (C01A); antiarrhythmic drugs (C01B); laxatives (A06A); proton pump inhibitors (A02BC); antiparkinson drugs (N04); acetylcholinesterase inhibitors (N06DA); beta blocker eye drops (S01ED); corticosteroid (H02A); oral

hypoglycaemic drugs (A10B); vitamin D (A11CC05); nonsteroidal anti-inflammatory (NSAID) drugs (M01A); fluoroquinolones (J01MA); and antineoplastic agents (L01).

Confounding covariates:

Many different risk factors and predictors for falls in older adults have been described previously and classified into different domains: sociodemographic, medical conditions, psychological, balance and mobility, and medication use (4,25,26). All these risk factors are possible confounders to the potential FRIDS; hence, the following a priori list specifies the confounding variables to be adjusted for in the multivariate regression model:

- Age (5,8).
- Sex (4).
- History of previous falls (19,27,28).
- The comorbidity related to the potential FRID to adjust for confounding by indication (18).
- Fear of falling using Short Falls Efficacy Scale-International 7-item (4,27–30).
- Gait speed measured with a 4-meter walk test (31–33).
- Cognitive impairment estimated by the Orientation-Memory-Concentration test performed over the telephone (4,27,33,34).
- Frailty using the Tilburg Frailty Indicator (35).
- Physical and instrumental disability in activities of daily living using the Vulnerable Elders Survey 13 (4,32,33,36).
- Depressive symptoms using Geriatric Depression Scale 4 item, a depression diagnosis or prescription of any antidepressants (4,16,27,28).
- Use of benzodiazepines, benzodiazepines derivatives or non-benzodiazepines (Z-drugs) (16,37).
- Use of opioids (15,38).

Statistical analysis

Outcome:

The primary outcome is fall rate per person-year. Fall rate will be calculated as the total number of falls divided by length of follow-up in years. A fall was defined as "an unexpected event in which the participants come to rest on the ground, floor, or lower lever" (39). Falls were recorded

prospectively with daily fall calendars with a monthly reporting and validated by a phone call if a fall was registered. If the calendar was not received within 14 days after deadline, the participant was contacted to retrieve the missing data.

Statistical methods:

A flowchart will be given to illustrate the flow of participants through the study including number of participants with and without falls. The participants' baseline characteristics and follow-up time will be summarised using descriptive statistics. Continuous variables will be summarized using medians with interquartile range, and categorical variables will be presented using counts and percentage proportions. Furthermore, the number of participants with missing data for the outcome, baseline characteristics, and confounding covariates will be presented. Then, missing data will be handled with multiple imputation methods. Finally, a univariate and multivariate Poisson regression model will be used to specify the association (expressed as incidence rate ratio, IRR) between the potential FRID and the rate of falls. For each potential FRID, a multivariate Poisson regression model will be performed adjusting for the medical indication of each drug and all other confounders from the a priori list. However, the Poisson regression model will only be performed for the potential FRID if more than 5 participants have a prescription registered at baseline. P-values lower than 0.05 will be considered as statistically significant. All statistical analyses will be carried out using R, version 4.0.2, (R Foundation).

Dissemination and reporting

The investigators want to publish the study in peer-reviewed journals in English. The reporting of the study will follow the Strengthening the Reporting of Observational studies in Epidemiology (STROBE) statement.

References:

- 2. Organization WH. WHO Global report on Falls Prevention in Older Age. Community Health. 2007.
- 3. EuroSafe. Injuries in the European Union, Summary on Injury Statistics 2012-2014. Amsterdam; 2016.
- 5. Rubenstein LZ. Falls in older people: Epidemiology, risk factors and strategies for prevention. Age Ageing. 2006;35(SUPPL.2):37–41.

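### The plan states a 1-year follow-up, but its rule for person-time runs to 18/07/2020 with no 1-year limit, so falls and person-time may cover different windows

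*Combined protocol and SAP*

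**What the plan says.** The Primary objective concerns the "falls rate with a 1-year followup in a cohort" of community-dwelling older adults. Under Study design and sample size the plan adds: "The study recruited participants from 14/06/2018 to 18/07/2019 and had a 1-year follow-up period".

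The Follow-up paragraph, under Study population and setting, gives the only rule for computing person-time: "Follow-up time will be defined as the time from inclusion until death, withdrawal, or end of the study at the 18/07/2020". It names three end events, and one year after inclusion is not among them.

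Under Outcome, this time becomes the denominator of the primary outcome: "Fall rate will be calculated as the total number of falls divided by length of follow-up in years". Falls were recorded "prospectively with daily fall calendars with a monthly reporting and validated by a phone call if a fall was registered". The plan does not say when a participant's calendars stopped.

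The Statistical methods section specifies Poisson regression with results as incidence rate ratios (IRRs). It names neither an offset nor a time window.

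**The concern.** A rate per person-year is valid only if its falls and its person-time cover the same window. The plan states one year in two places and defines a longer period in a third, and the third is the one an analyst would code. If falls come from one year of calendars while person-time runs to the fixed end date, the denominator is too long, and it is longest for the earliest recruits. The named primary outcome would then be understated. The IRR would also move if users and non-users of a drug differed in entry date or in attrition.

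**Working it through.** **Inputs from the documents.** First inclusion 14/06/2018, last inclusion 18/07/2019, study end 18/07/2020, stated follow-up 1 year, stated inclusion period 13 months. Recruitment shape and loss to follow-up are not given, so they are assumed below and varied.

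**The plan's own figure.** 14/06/2018 to 18/07/2019 is 399 days, and 399 / 30.4375 = 13.1 months. The stated 13 months reproduces.

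**Person-time for a completer under the Follow-up rule.**
- First recruit: 14/06/2018 to 18/07/2020 = 765 days (765 / 365.25 = 2.09 years).
- Last recruit: 18/07/2019 to 18/07/2020 = 366 days (1.00 year).

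Every inclusion date before the last gives more than 366 days, so the rule and the 1-year statements agree only for the final recruits.

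**Understatement if falls cover 365 days but person-time follows the written rule.** For a completer with written time T days, the understatement is 1 − 365/T.
- Last recruit: 1 − 365/366 = 0.003, or 0.3%.
- First recruit: 1 − 365/765 = 0.523, or 52%.

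This range needs no assumption about recruitment shape.

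**Overall rate (total falls over total person-time), no loss.** The mean written time is 765 days minus the mean entry delay.

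| Assumed entry pattern | Mean entry delay (days) | Mean written time (days) | Understatement |
|---|---|---|---|
| Uniform | 399/2 = 199.5 | 565.5 | 1 − 365/565.5 = 35% |
| Rising linearly from zero | 399 × 2/3 = 266 | 499.0 | 1 − 365/499.0 = 27% |
| Falling linearly to zero | 399 × 1/3 = 133 | 632.0 | 1 − 365/632.0 = 42% |

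**Sensitivity to loss.** Assume 20% are lost in year 1 at a constant hazard and none afterwards. Mean time within the first year is 0.20 × 365 / (−ln 0.80) = 327.1 days. Under uniform entry the mean written time is 327.1 + 0.80 × (565.5 − 365) = 487.5 days, and the understatement is 1 − 327.1/487.5 = 33%. The rising and falling patterns give 434.3 and 540.7 days, or 25% and 40%.

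**IRR.** If drug use is unrelated to entry date and attrition, the excess person-time is proportionally the same in users and non-users, and the IRR is multiplied by 1.00. As a hypothetical illustration only, suppose users joined on average 30 days earlier. The unadjusted IRR would be multiplied by (565.5 − 15)/(565.5 + 15) = 550.5/580.5 = 0.95. This assumes that the log of the written follow-up time is the offset, which the plan does not state.

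**If the windows already match.** If calendars ran to 18/07/2020 for everyone, or if the analyst applies an unwritten 1-year cap, the understatement is 0%.

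**The case against.** The strongest reply is that 18/07/2020 is simply the day the last participant finished. It falls exactly one year after the last inclusion, the plan states one year twice, and the parent study's titles in the reference list also refer to 1-year risk. On that view each person was followed for one year and the Follow-up sentence is merely incomplete. This is probably what was meant, and it makes calendars running to 18/07/2020 for everyone unlikely. But it does not rescue the sentence. The more likely it is that falls were collected for one year, the more likely it is that literal coding gives the wrong denominator.

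A second reply is that the objective concerns an association, which the plan expresses as an IRR, and the IRR need not move. That stands. A reader might infer from the 35% that the drug associations are biased, but the documents give no data linking drug use to entry date or attrition. The several recruitment channels are a reason not to presume independence; they are not evidence of dependence. The fall rate itself, which the plan names as its primary outcome, gains nothing from this cancellation.

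A third reply is that the error would be noticed. The Statistical methods section says that "baseline characteristics and follow-up time will be summarised using descriptive statistics", and it places this step before imputation and before the Poisson models. Follow-up times near two years could therefore be seen before any model is fitted. This is a genuine safeguard, and it would be wrong to say that they would come to light too late. It still depends on someone noticing, and the written rule would still need correcting.

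Finally, the parent study's own documents may give the calendar stop date. That is possible, but this plan does not state it.

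**Conclusion.** The concern holds as a conflict between a written rule and the stated design. The 1-year statements and the Follow-up definition cannot both be true for nearly all completers, and nothing else in the plan reconciles them.

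The size is conditional. With 1-year collection and literal use of the rule, a single completer's rate is understated by 0.3% to 52%. The overall rate is understated by about 35% with uniform entry and no loss, and by 27% to 42% if entry is skewed. Assumed loss of 20% in year 1 changes these to 33% and 25% to 40%. If the windows in fact match, there is no understatement.

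Two stronger readings are not supported. The documents do not show that the fall rate will be wrong, because they do not say when calendars stopped or how the rule will be coded. They also do not show that any IRR is biased. The point is worth settling before the analysis because it concerns the definition of the primary outcome and is easy to correct.

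**What to change.** First confirm the collection window. The plan says "All study data were accessible from the PREFALL study before the completion of this protocol", so the last calendar dates can be checked now, without analysing the outcome. Then use one identical window for falls and person-time.

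- **If collection was one year per person:** define follow-up as inclusion to the earliest of one year, death, withdrawal or 18/07/2020. Count only falls within that window, and state the log of that time as the Poisson offset.
- **If calendars ran to 18/07/2020 for everyone:** keep the Follow-up rule, state the same kind of log-time offset, and correct the 1-year wording in the objective and the design section.

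Leave missing calendars within the window to the plan's existing handling, which is contact with the participant and then multiple imputation. Ending follow-up at the last returned calendar would bring in a different missing-data rule that the plan does not call for.

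The cost is one sentence and one recalculated date variable, with no new data. If the cap applies, mean nominal person-time per completer falls from about 566 days (499 to 632 across the assumed entry patterns) to 365. If calendars ran longer, a cap would discard observed falls, so the window must be confirmed first.

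### The adjusted model for oral hypoglycaemics (A10B) has no insulin term, so participants with diabetes on insulin alone count as unexposed and the IRR may be biased, usually towards attenuation

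*Combined protocol and SAP*

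**What the plan says.** - **Exposure.** In the Baseline medication section the item runs over a page break: "corticosteroid (H02A); oral" is followed by "hypoglycaemic drugs (A10B); vitamin D (A11CC05". The class is thus oral hypoglycaemics, ATC A10B. Insulin (A10A) is not on the list.
- **Indication.** The Confounding covariates section lists "The comorbidity related to the potential FRID to adjust for confounding by indication". For A10B this is by implication diabetes, which is not named.
- **Model.** The Statistical methods section sets one rule that applies to every class in turn: "a multivariate Poisson regression model will be performed adjusting for the medical indication of each drug and all other confounders from the a priori list". The plan does not say that the candidate drug classes are adjusted for one another.
- **Drug covariates.** The a priori list contains antidepressants (inside the depression item), opioids, and "Use of benzodiazepines, benzodiazepines derivatives or non-benzodiazepines (Z-drugs) (16,37"). None of these captures insulin.
- **Eligibility and data.** None of the four exclusions under Study population and setting concerns diabetes or insulin. Diagnoses come from hospital records (Baseline characteristics). All medication in the Shared Medication Record at baseline was ATC-coded, so insulin users can be identified.

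**The concern.** Once diabetes is in the model, the A10B coefficient comes mainly from comparing A10B users with people who have diabetes and take no A10B drug. That comparator mixes people on no glucose-lowering drug with people on insulin alone. The exposed group likewise mixes A10B alone with A10B plus insulin. The adjusted IRR then answers neither A10B against no treatment nor A10B against insulin.

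Insulin-only users in the reference group pull the IRR down if they fall more often, and co-users in the exposed group push it up. The net direction cannot be read from the fitted model. At stake is one class-level conclusion: an IRR near 1 could be taken as evidence that oral hypoglycaemics do not raise fall risk when part of the signal has been absorbed by insulin.

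**Working it through.** The plan states no sample size, power, expected IRR or treatment count, so there is no figure of its own to reproduce. Every input below is an assumption.

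**Formula.** If every A10B user carries a diabetes code, the adjusted IRR is a contrast within diabetes:

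IRR_est = b × [1 + q1(R − 1)] / [1 + q0(R − 1)]

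- b: true A10B IRR against untreated diabetes
- R: rate ratio for insulin against no insulin in diabetes, remaining after the planned covariates
- q1: insulin share among A10B users
- q0: insulin share among people with diabetes and no A10B

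IRR_est equals b if R = 1, if q0 = q1, or if there are no insulin users. It is below b when R > 1 and q0 > q1.

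**Results for b = 1.30, q1 = 0.15.** The numerators are 1.30 × 1.03 = 1.339 (R = 1.2), 1.30 × 1.075 = 1.3975 (R = 1.5) and 1.30 × 1.15 = 1.495 (R = 2).

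| q0 | R = 1.2 | R = 1.5 | R = 2 |
|---|---|---|---|
| 0.10 | 1.339/1.02 = 1.31 | 1.3975/1.05 = 1.33 | 1.495/1.10 = 1.36 |
| 0.30 | 1.339/1.06 = 1.26 | 1.3975/1.15 = 1.22 | 1.495/1.30 = 1.15 |
| 0.50 | 1.339/1.10 = 1.22 | 1.3975/1.25 = 1.12 | 1.495/1.50 = 1.00 |
| 0.70 | 1.339/1.14 = 1.17 | 1.3975/1.35 = 1.04 | 1.495/1.70 = 0.88 |

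A weighted Poisson model with a diabetes term (diabetes prevalence 14%, 70% of people with diabetes on A10B, diabetes rate ratio 1.2) gives the same values. Adding an insulin term returns 1.30 in every cell.

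**When the signal is lost.** IRR_est = 1 at q0 = {b[1 + q1(R − 1)] − 1}/(R − 1). For b = 1.30 this is 0.3975/0.5 = 80% at R = 1.5 and 0.495/1 = 50% at R = 2.

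**Sensitivity to co-use, b = 1.30, q0 = 25%, 50%, 75%.** With no co-use, IRR_est is 1.16, 1.04, 0.95 (R = 1.5) and 1.04, 0.87, 0.74 (R = 2). With 20% co-use it is 1.27, 1.14, 1.04 and 1.25, 1.04, 0.89, so only one of these six values is below 1.

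**Incomplete diabetes coding.** Suppose hospital records capture 70% of diabetes not treated with insulin and 95% of insulin-treated diabetes (b = 1.30, R = 2, q1 = 0.15). The adjusted IRR for q0 = 0.30, 0.50, 0.70 is then 1.35, 1.23, 1.13 without an insulin term and about 1.43 with one. The omission still attenuates but does not reverse. The 1.43 exceeds 1.30 because missed diabetes leaves confounding by indication.

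**Univariate IRR.** In the same settings it moves only from 1.75 to 1.71 as q0 goes from 0.30 to 0.70, because most non-users have no diabetes.

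**Precision.** Take 100 people with diabetes, 70 on A10B, 14 of these also on insulin, and equal fall rates. The planned model has a variance of the log IRR proportional to 1/70 + 1/30, that is, information 21.0. With an insulin indicator, the information from the two insulin strata adds up:

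- q0 = 25%: 1/(1/56 + 1/22.5) + 1/(1/14 + 1/7.5) = 16.05 + 4.88 = 20.9; SE +0%
- q0 = 50%: 1/(1/56 + 1/15) + 1/(1/14 + 1/15) = 11.83 + 7.24 = 19.1; SE +5%
- q0 = 75%: 1/(1/56 + 1/7.5) + 1/(1/14 + 1/22.5) = 6.61 + 8.63 = 15.2; SE +17%

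Using only the stratum without insulin (first term alone) raises the SE by 14%, 33% and 78%.

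**The case against.** The strongest reply is that the bias needs several conditions at once. Diabetes must be well recorded, although it comes from hospital records only. Insulin must keep an effect after adjustment for previous falls, gait speed, frailty, disability, cognition, fear of falling, depression and the other listed covariates; only that residual effect matters, and it may be close to 1. Insulin-only users must be a large share of people with diabetes and no A10B. Co-use in the exposed group offsets part of the bias. The model is one of 16 possible class models, none designated as primary, and the contaminated reference group hardly touches the univariate IRR.

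All of this stands as a limit on size. It does not remove the structural fault. With incomplete coding the IRR is still pulled down. The univariate IRR is no substitute, since it carries the confounding by indication that the adjusted model is meant to remove.

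A reader might also infer that insulin was meant to be studied, because the introduction names "hypoglycaemics, fluoroquinolones, corticosteroids, and nonsteroidal anti-inflammatory drugs" without qualification and speaks of wanting "to achieve a better understanding of these 17 medication classes as potential FRIDs". The documents do not support that. The second statement is a general call for more studies. The objective refers to the potential FRIDs, which the Baseline medication section then lists. The introduction uses broad labels throughout, and whether its word for this class included insulin depends on a cited paper outside the documents. Restricting the exposure to oral drugs is a legitimate choice, and the number of classes listed is not a fault here.

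**Conclusion.** The point holds in limited form. The plan's coding rule places insulin-only users with diabetes among the unexposed and does not separate insulin co-users. The adjusted A10B IRR is biased if insulin has a residual effect on falls and its use differs between A10B users and non-users with diabetes. When insulin raises falls and is commoner among non-users, the IRR is pulled down. Under the illustrative inputs with a residual insulin rate ratio of 1.5, a true 1.30 reads as 1.22 to 1.04 for insulin shares of 30% to 70%. If insulin is less common among non-users than among users, the bias is small and upward (1.33 at a 10% share).

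A reader might go further and infer that the class's IRR will be cancelled or reversed. The documents do not support that. It would take near-complete diabetes coding together with, for example, a doubled residual fall rate on insulin and insulin in about half or more of non-users with diabetes. The size rests entirely on assumed shares and rate ratios; if the cohort has no insulin users, there is no bias. The change is worth making because it is cheap and the data are held.

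**What to change.** In the A10B model, add baseline insulin use (A10A, yes/no) as a covariate alongside the diabetes term. Report how many participants with diabetes use A10B only, insulin only, both, and neither. If insulin users are too few to fit the term, leave them out of this one model instead of counting them as unexposed. Write this into the plan before any outcome analysis, since the data are already accessible.

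The cost is a recode of ATC data already held, one more coefficient, and a somewhat wider interval (0 to 17% in the SE of the log IRR under the assumptions above). The indicator also assumes that the A10B IRR is the same with and without insulin; the four counts show how much the estimate leans on that. Mutually exclusive treatment groups would avoid the assumption, but at the larger loss of precision shown above (14 to 78%), so the indicator is preferable here.

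### Each exposure is defined by a single ATC code, so users of the same substance under another code, most clearly vitamin D, would not be counted as exposed

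*Combined protocol and SAP*

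**What the plan says.** Under Baseline medication, everything registered for a participant in the national Shared Medication Record (SMR) at inclusion is documented and "indexed according to the WHO-recommended anatomical therapeutic chemical (ATC) medication classification system". The section then lists 16 potential fall-risk-increasing drugs (FRIDs), each with one code. The list begins "Beta-blockers (C07A); angiotensin-converting enzyme (ACE) inhibitors (C09A); calcium channel blockers (C08" and includes "vitamin D (A11CC05", "antiparkinson drugs (N04" and "antineoplastic agents (L01".

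The Primary objective is worded in terms of using these drugs, not of using single-substance products. Statistical methods fits a separate multivariate Poisson model for each FRID, reports an IRR, and fits a model only when more than 5 participants have a registered prescription.

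The plan does not say how fixed combinations are classified, what happens when the same substance appears under another code, or who makes up the unexposed group in each model.

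**The concern.** The code list is the exposure definition, so any gap between label and code goes straight into the primary estimate. For vitamin D the gap is visible in the text: a class name is attached to a code at the depth of one entry in a hierarchical index. A vitamin D user registered under a different code is not captured and, unless the plan says otherwise, is compared with the captured users as though not taking vitamin D.

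The same can happen in any class whose substances are also sold in fixed combinations coded elsewhere. Beta-blockers and ACE inhibitors are the examples to check first.

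Two things are at stake. The IRR may be distorted, and the exposed group shrinks by the share of users who are missed. The background section also gives imprecise drug definitions in earlier studies as a reason for doing this one.

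**Working it through.** **What the code list shows.** Counting characters in the 16 codes:

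- three characters: C08, N04, L01 (3 codes)
- four characters: C07A, C09A, C01A, C01B, A06A, H02A, A10B, M01A (8 codes)
- five characters: A02BC, N06DA, S01ED, J01MA (4 codes)
- seven characters: A11CC05 (1 code)

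Vitamin D is the only outlier. C07A and C09A are at the commonest depth, so depth alone shows nothing wrong with them. The list does show that one drug class can sit under more than one code: beta-blockers appear as C07A and, as eye drops, as S01ED. The plan splits those openly but has no rule for combinations.

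**Size, for scale only.** The plan gives no cohort size, user counts or expected IRR, so there is no figure of its own to reproduce. All inputs are assumptions:

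- R = true IRR = 1.5
- p = true share of the cohort using the class = 0.2 or 0.4
- m = share of those users whose product is coded elsewhere = 0.1, 0.3, 0.5 or 0.7
- equal follow-up, no confounding, and missed users with the same fall rate as captured users

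Share of the comparison group who are really users: f = p·m / [(1 − p) + p·m].

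Observed IRR = R / [(1 − f) + f·R].

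Worked case, p = 0.4 and m = 0.1: f = 0.04 / (0.60 + 0.04) = 0.0625. Observed IRR = 1.5 / (0.9375 + 0.09375) = 1.5 / 1.03125 = 1.4545.

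| Share missed (m) | f, p = 0.4 | IRR, p = 0.4 | f, p = 0.2 | IRR, p = 0.2 |
|---|---|---|---|---|
| 10% | 0.0625 | 1.45 | 0.0244 | 1.48 |
| 30% | 0.1667 | 1.38 | 0.0698 | 1.45 |
| 50% | 0.2500 | 1.33 | 0.1111 | 1.42 |
| 70% | 0.3182 | 1.29 | 0.1489 | 1.40 |

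Over the same range of m, the observed IRR runs from 1.49 to 1.45 at 10% true use and from 1.43 to 1.24 at 50%. The loss is small for a little-used class and larger for a common one. The exposed count falls by m in every case.

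**Direction.** If missed users have a rate ratio S different from R, the observed IRR is R / [(1 − f) + f·S]. With S = R it moves toward 1, as in the table. With S = 1 it does not change. With S below 1 it moves away from 1. Users of a fixed combination also take a partner drug, so S = R cannot be taken for granted.

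**The more-than-5 rule.** At p = 0.2 and m = 0.7, the code captures 0.2 × 0.3 = 6% of the cohort, so expected users fall below 6 only if the cohort is under 100. At p = 0.4 and m = 0.7 the code captures 12%, and the limit is a cohort under 50. These scenarios give no ground for saying that a class would be dropped.

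**The case against.** The strongest reply is that the plan names the ATC index without reproducing it. That beta-blockers, ACE inhibitors or vitamin D occur under further codes is a fact about the index, and nothing in the documents shows that any participant uses only such a product. This stands, and is why the classes other than vitamin D are a matter to check.

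A reader might infer from the mixed code depths that the list is too narrow throughout, or that C07A and C09A are plainly too narrow beside C08. The documents do not support that. Drug classes occupy different levels of a hierarchy, and C08 too would miss a calcium channel blocker in a product coded in another group.

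A reader might also infer that the plan expressly counts these users as unexposed. It does not, because the comparator is never defined. Placing them there is the natural reading of one model per FRID.

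Finally, a single-code definition is explicit and reproducible, whereas counting combinations brings in the partner drug's effect. The a priori list under Confounding covariates contains no other potential FRIDs, so widening exposure also means changing the affected models. That is a real cost, but a manageable one. It does not justify labelling one code as vitamin D.

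**Conclusion.** The point holds. Each exposure is set by one code, and for vitamin D the label and the code do not match. Under the rule as written, a user whose only product carries another code is not counted as exposed and would most naturally enter the comparison group. Whether other classes are affected depends on the ATC index.

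The actual size is unknown. Under the assumptions shown, a true IRR of 1.5 would be observed as 1.45 to 1.29 at 40% true use and as 1.48 to 1.40 at 20%, with 10% to 70% of users missed. The figures below about 1.4 need a commonly used class and a substantial share of users missed, for which the documents give no basis. Movement toward 1 requires missed and captured users to have similar fall risk.

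Two stronger conclusions are not supported: that the bias is certainly toward 1, and that a class would fail the more-than-5 rule because of its code. The change is worth making because this is the primary exposure and the data are already held.

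**What to change.** Before the outcome analysis:

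1. Define exposure by substance. A participant is exposed if any SMR-registered product contains a substance of the class, alone or in a fixed combination, whatever its code. A combination counts as exposure to each component. Keep the plan's existing separation of beta-blocker eye drops as its own exposure.
2. List, for each FRID, every code that counts, after checking the ATC index.
3. Define the unexposed group in each model as participants with no such product.
4. For vitamin D, either include all vitamin D and vitamin D-calcium products, or rename the exposure as the single substance and remove users of other vitamin D products from its comparison group.
5. Where combinations add exposed participants, adjust for the partner drug in the affected models, and report the present single-code definition as a sensitivity analysis.

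The cost is a longer code list, an added covariate in some models and one extra set of results. All SMR medication is already recorded and ATC-indexed, so no new data are needed. The downside is that combination users carry two exposures, and adjustment separates these only as far as enough participants take one component without the other.
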